## List of abbreviations

AE	Adverse event
BDCAF	Behçet's Disease Current Activity Form
SAE	Serious adverse event
CRF	Case Report/Record Form (paper or electronic)
CNS	Central Nervous System
CPO	Country Pharma Organization
CRO	Contract Research Organization
CSF	Cerebrospinal Fluid
EDSS	Expanded Disability Status Scale
ICH	International Conference on Harmonization of Technical Requirements for Registration of Pharmaceuticals for Human Use
IEC	Independent Ethics Committee
i.v.	intravenous
IRB	Institutional Review Board
NBDS	Neuro-Behçet's disease
Modified EDSS	Modified Expanded Disability Status Scale
VAS	Visual Analog Scale
IV MP	Intravenous Methyl Prednisolone
PK/PD	Pharmacokinetics/ Pharmacodynamic

## SAE Serious adverse event Glossary of terms

Assessment	A procedure used to generate data required by the study
Cohort	A group of newly enrolled patients treated at a specific dose and regimen (i.e. treatment group) at the same time
Control drug	Any drug (an active drug or an inactive drug, such as a placebo) which is used as a comparator to the drug being tested in the trial
Dose level	The dose of drug given to the patient (total daily or weekly etc.)
Enrollment	Point/time of patient entry into the study at which informed consent must be obtained (i.e. prior to starting any of the procedures described in the protocol)
Epoch	A portion of the study which serves a specific purpose. Typical Epochs are: screening/recruitment, wash-out, treatment, and follow-up
Investigational drug	The drug whose properties are being tested in the study; this definition is consistent with US CFR 21 Section 312.3 and is synonymous with "investigational new drug" or "investigational medicinal product."
Investigational treatment	All investigational drug(s) whose properties are being tested in the study as well as their associated treatment controls. This includes any placebos, any active controls, as well as approved drugs used outside of their indication/approved dosage or tested in a fixed combination. Investigational treatment generally does not include protocol-specified concomitant background therapies when these are standard treatments in that indication
Medication number	A unique identifier on the label of each investigational/study drug package in studies that dispense medication using an IRT system
Protocol	A written account of all the procedures to be followed in a trial, which describes all the administrative, documentation, analytical and clinical processes used in the trial.
Part	A single component of a study which contains different objectives or populations within that single study. Common parts within a study are: a single dose part and a multiple dose part, or a part in patients with established disease and in those with newly-diagnosed disease.
Period	A subdivision of a cross-over study
Premature subject/patient withdrawal	Point/time when the patient exits from the study prior to the planned completion of all study treatment administration and/or assessments; at this time all study treatment administration is discontinued and no further assessments are planned, unless the patient will be followed for progression and/or survival
Randomization number	A unique identifier assigned to each randomized patient, corresponding to a specific treatment arm assignment
Study drug/ treatment	Any single drug or combination of drugs administered to the patient as part of the required study procedures; includes investigational drug (s), active drug run-ins or background therapy
Study/investigational treatment discontinuation	Point/time when patient permanently stops taking study/investigational treatment for any reason; may or may not also be the point/time of premature patient withdrawal
Subject Number	A number assigned to each patient who enrolls into the study
Variable	A measured value or assessed response that is determined in specific assessments and used in data analysis to evaluate the drug being tested in the study

## Protocol summary

Protocol number	CACZ885NTR01
Title	An open label, exploratory study to establish the efficacy and safety of 1 year Canakinumab treatment in Behçet's Disease Patients with Neurologic or Vascular Involvement
Brief title	Efficacy and Safety of Canakinumab in Behçet's Disease Patients with Neurologic or Vascular Involvement
Sponsor and Clinical Phase	Novartis Phase 2 Exploratory Study
Investigation type	Drug
Study type	An open label Phase 2 Study
Purpose and rationale	Study objective is to evaluate efficacy and safety of canakinumab in neurologic and vascular subtypes of Behçet's disease (BD).
Primary Objective(s)	Primary objective of the study is to evaluate the safety and efficacy of canakinumab on the clinical and inflammatory findings of BD patients with neurologic and vascular involvement.
Secondary Objectives	Secondary objectives include analyses measuring the effects of canakinumab on radiological findings (neurologic and vascular), cerebrospinal fluid (CSF) findings (neurologic), and [REDACTED] [REDACTED] aiming to investigate the biology of inflammatory attacks and their response to IL-1 blockade in parallel with clinical findings.
Study design	The study will be conducted as an exploratory open-label pilot trial. There will be only one treatment arm. The improvement will be evaluated in comparison to the findings recorded at the baseline.
Population	Biologic naïve patients aged over 18 with BD fulfilling the International Study Group (ISG) criteria, who have a recent exacerbation of large-vessel vascular disease and/or parenchymal neurologic disease (within the last month).
Inclusion criteria	
For NBS :1) Patients experiencing an acute exacerbation of parenchymal neurologic disease involving brainstem and/or diencephalic region with in last month.
 
Exacerbation is defined based on the presence of both of the following:
 
 
a. An acute/subacute neurological syndrome including any of hemiparesis, ataxia, dysarthria within the first month
 

	
of onset of neurologic manifestations (without any prior high dose steroid treatment)
 
b. Compatible cranial MRI lesion involving brainstem and/or diencephalic region
 
2) Patients aged over 18-60 BD fulfilling the International Study Group (ISG) criteria, who have exacerbation of large-vessel vascular disease and/or parenchymal neurologic disease with in last month.
 
For Vascular Disease :
 
1)Patients experiencing an acute exacerbation of vascular disease within the last month, involving
 
a. Large arteries (abdominal aorta, pulmonary arteries, extremity arteries)
 
b. Large veins (deep vein thrombosis of extremities, caval vein thrombosis, dural sinus thrombosis)
 
c. Compatible radiological findings (spiral CT, MR, or Doppler ultrasonography)
 
2) Patients aged over 18-60 BD fulfilling the International Study Group (ISG) criteria, who have exacerbation of large-vessel vascular disease and/or parenchymal neurologic disease with in last month.

Exclusion criteria	
For NBS:
 

1. Presence of severe neurological sequelae from any previous attacks rendering the patient dependent on others physically or mentally

2. Any other neurological cause underlying the picture including ischemic CNS lesion on MRI

3. Any previous treatment with biological agents other than interferon-alpha or any previous treatment with cyclophosphamide

**For Vascular disease**

4-Presence of severe vascular sequelae from any previous attacks rendering the patient dependent on others

5-Any other vascular disease complication the evaluation of exacerbation

6-Any previous treatment with biological agents other than interferon-alpha, or any previous treatment with cyclophosphamide

**General**

7- Presence or history of any other inflammatory rheumatic disease

8- Use of the listed treatment

- a. interferon-alpha in the last 6 months,
- b. IVMP in the past month

9- Positive PPD test (according to local guidance) where an active TB infection cannot be excluded via Quantiferon (T-Spot or radiographic imaging if needed) If PPD test or Quantiferon-Gold assay result shows latent TB infection without signs of active tuberculosis disease, patient will be allowed to enter in the study, when the patient agrees to start taking isoniazid prophylaxis along with the study drug for 9 months.

10- Pregnancy or lactation

11-Presence of any active or chronic infection or any major episode of infection requiring hospitalization or treatment with i.v. antibiotics within 30 days or oral antibiotics within 14 days prior to screening

12-History of a malignancy within the last 5 years, except for successfully excised squamous or basal cell carcinoma of the skin

13-Women of childbearing potential not using the contraception method(s) specified in this study, as well as women who are breastfeeding

14-With known sensitivity to canakinumab

15- Use of any other investigational agent in the last 30 days

Investigational and reference therapy	Canakinumab
Efficacy assessments	Resolution of attacks Prevention of recurrent attacks Need for steroid usage Control of the symptoms
Safety assessments	All AEs and SAEs will be recorded appropriately.
Other assessments	PK/PD data will be collected. Canakinumab [REDACTED] will be measured in CSF.
Data analysis	All improvements in the [REDACTED] outcomes will be compared to the baseline, and statistical analyses will be conducted when possible.
Key words	Behcet's disease, Neuro-Behcet Syndrome, Disease Exacerbation, IL-1 Blockade, Canakinumab, CNS inflammation, Vasculitis

## 1 Introduction

### 1.1 Background

BD is a multisystem inflammatory disorder characterised by relapsing/remitting manifestations with variable vessel vasculitis as the underlying pathology. Prevalence of BD is in a wide range between 1-420 / 100,000 depending on geographic region in the world.

Some courses of the disease carry a higher unmet need:

a. Neurologic involvement: The patients experiencing parenchymal neurologic inflammatory attacks mainly affecting the brainstem have serious morbidity and increased mortality. There is no established treatment or a clinical trial conducted to evaluate the efficacy of any drug in Neuro-Behçet disease (NBD).

b. Vascular disease: Depending on the involved large vessels (arteries and/or veins), vascular involvement has also been associated with increased morbidity and mortality. Similar to NBD there is no established treatment or a clinical trial conducted to evaluate the efficacy of any drug in large vessel vasculitis.

In recent years, some case reports showed the efficacy of canakinumab in different BD manifestations. (1,2,3,4)

Vitale et al. reported that the prompt and sustained clinical efficacy of canakinumab as a monotherapy in patients with BD supports the opportunity of using this specific anti-IL-1 $\beta$  agent as a valid therapeutic option for those cases showing a disease course resistant or refractory to multiple treatments. (1)

Cantarini et al. reported the results of canakinumab treatment in a refractory patient with BD, which was well-tolerated, and at the 6-month follow-up, no adverse events were noted. (2)

### 1.2 Purpose

Study objective is to evaluate the efficacy and safety of canakinumab in neurologic and vascular subtypes of BD.

## 2 Study objectives

**Primary objective:** Primary objective of the study is to evaluate the safety and efficacy of canakinumab on the clinical and inflammatory findings of BD patients with neurologic and vascular involvement.

**Secondary objectives:** Secondary objectives include analyses measuring the effects of canakinumab on radiological findings (neurologic and vascular), cerebrospinal fluid findings (neurologic), and [REDACTED] aiming to investigate the biology of inflammatory attacks and their response to IL-1 blockade in parallel with clinical findings.

## 2.1 Primary objective(s)

**Primary endpoint:** Resolution of acute exacerbation findings related to BD based on achievements in any of the following items without deterioration on day 30:

**For patients with parenchymal neurologic disease:** Resolution of acute exacerbation of parenchymal neurologic findings based on improvements in any of the following items without deterioration on Day 30:

- a. Improvement of muscle strength, ataxia, or other relevant neurologic findings depending on the involved region on neurological examination (by NBDS, Modified EDSS, and modified Rankin scores)
- b. Improvement in systemic inflammatory findings (CRP, ESR, SAA)
- c. Any decrease in the size of the MRI lesion, or disappearance of contrast enhancement
- d. Improvement in patients' and physicians global assessment using a 10-cm visual analogue scale (VAS)

**Complete response** will be defined as full clinical recovery to the pre-attack state, disappearance of MRI lesion(s), and normalisation of CSF findings.

**Partial response** will be defined as partial improvement in clinical findings, but with findings still worse than the pre-attack state, and MRI lesions, which become smaller with no or less enhancement, and a decrease in CSF cell count.

**Non-response** will be defined as no improvement in clinical findings, no change on MRI, no change in CSF parameters, or worsening in those findings.

**For patients with large vessel vascular disease:** Resolution of acute vascular exacerbation findings related to BD based on achievements in any of the following items without deterioration at 1 month:

- a. Improvement in relevant symptoms (localised pain, abdominal pain, calf thickness, haemoptysis) by using physician and patient's global assessment with VAS
- b. Improvement in systemic inflammatory findings (CRP, ESR, SAA)
- c. Any improvement in radiological findings depending on the involved vessels (MR, CT or Doppler findings)
- d. Improvement in patients' and physicians global assessment using a 10-cm visual analogue scale (VAS)

**Complete response** will be defined as clinical and laboratory improvement based on  $\geq 50\%$  improvements in patient's and physician's global assessments by using VAS, and  $\geq 50\%$  reduction in CRP values; along with stable or  $\geq 20\%$  reduced aneurym size in patients with arterial involvement, and stable or  $\geq 20\%$  reduced calf swelling in patients with lower extremity venous thrombosis.

**Partial response** will be defined as clinical and laboratory improvement based on observations of an improvement between 20-49% according to patient's and physician's global assessments by using VAS, 20-49% reduction in CRP values; along with stable or less than 20% reduced aneurym size in patients with arterial involvement, and stable or less than 20% reduced calf swelling in patients with lower extremity thrombosis.

**Non-response** will be defined as observing no or less than 20% clinical improvement by patient's and physician's global VAS or worsening of clinical findings, no change or increase in acute phase response, increase in aneurysm size for patients with arterial involvement or progression of venous thrombosis in patients with venous involvement.

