### 3 Investigational plan

#### 3.1 Study design

The study will be conducted as an exploratory open-label pilot trial. There will be only one treatment arm. The improvement will be evaluated in comparison to the findings recorded at the baseline.

Figure 3-1 Study design

Approximately 10 subjects aged 18 to 60 years, who sign an informed consent and meet all inclusion and exclusion criteria in the screening period will enter into the study. The first dose of canakinumab will be administered as 300 mg IV.

At the end of the first month, an analysis will be conducted to assess the complete, partial, and non-responders to canakinumab treatment by physician.

Partial responders will be able to take the 2nd canakinumab dose as 300 mg IV infusion at the first month then will continue the canakinumab treatment with 150 mg IV infusions at monthly intervals for 4 times. The complete responders will continue the canakinumab treatment with 150 mg IV infusions at monthly intervals for 5 times. Non-responder or deteriorating patients will be dropped from the study at the first month evaluations.

At month 6, the patients will be able to switch to SC injections or continue as IV infusions of 150 mg canakinumab for additional 6 monthly administrations. Non-responder or deteriorating patients will be dropped from the study at the first month evaluations.

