#### **1-For Neuro Behcet Attack**

- A Improvement of muscle strength (Measured by MRC, and VAS)
- B Ataxia (Measured by global assessment of Physician)
- C Modified EDSS (Modified Expanded Disability Status Scale) , Neuro-Behçet's Disability Score (NBDS) **ranging from 0-8 and the modified Rankin scores (0-6)**
- D Improvement in systemic inflammatory findings (CRP, ESR, SAA)
- E Any decrease in the size of the MRI lesion, or disappearance of contrast enhancement

**Complete response** will be defined as full clinical recovery to pre-attack state, disappearance of MRI lesion(s), CSF becomes normal.

**Partial response** will be defined as partial improvement in clinical findings, but with findings still worse than pre-attack state, MRI lesions which become smaller with no or less enhancement, and a decrease in CSF cell count.

**Non-response** will be defined as no improvement in clinical findings, no change on MRI, no change in CSF parameters, or worsening in those findings.

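### The primary 'resolution' endpoint accepts improvement of any size in any one item and is not linked to the response categories, so a patient can be resolved and also a dropped non-responder

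*Combined protocol and SAP*

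**What the plan says.** **Primary endpoint (2.1, repeated in 5.9.1).** It is "Resolution of acute exacerbation findings related to BD based on achievements in any of the following items without deterioration on day 30". Section 2.1 lists four items, a to d, for each subgroup: clinical findings or symptoms, inflammatory markers, imaging, and patient and physician global VAS. The neurologic imaging item accepts "Any decrease in the size of the MRI lesion, or disappearance of contrast enhancement", and the vascular imaging item likewise accepts any improvement. The other items ask for improvement without an amount. No item has to be clinical, and neither section says what counts as deterioration.

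**Response categories (same sections).** Vascular complete and partial response have cut-offs at 50% and 20% for VAS and CRP. The neurologic categories have none. Neurologic non-response is "no improvement in clinical findings, no change on MRI, no change in CSF parameters, or worsening in those findings". Vascular non-response begins with "no or less than 20% clinical improvement by patient's and physician's global VAS or worsening of clinical findings" and continues as a comma-separated list covering acute-phase response and then aneurysm size or venous thrombosis.

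**Consequence (3.1 and 5.5.5).** "Non-responder or deteriorating patients will be dropped from the study at the first month evaluations".

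**Timing and analysis.** Section 3.4 has the physician assess the primary endpoint and determine the categories at the end of month 1. Section 8.4.1 lists the percentage of complete responders among the primary variables. Section 8.4.2 words the efficacy claim in terms of attack resolution, aims for a response of 50% or more in half or more of the patients, and refers back to the category definitions.

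**The concern.** Two classifications of the same patient are made at the same assessment, and the plan gives no rule connecting them. One asks for a change of any size in any single item. The other uses different components and, for vascular patients, numerical cut-offs. If they can disagree, a patient can satisfy the named primary endpoint and be removed as a treatment failure.

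The second difficulty is the size of change. With no floor for improvement and no definition of deterioration, random variation in CRP, lesion size or a VAS can satisfy the endpoint in a patient whose disease has not changed.

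This matters more here than in a controlled trial. The study is open-label with one arm, the physician makes the assessment, and section 7.5 requires no adjudication committee. Patients enter within a month of an acute exacerbation, so some spontaneous improvement is also possible. The definition of the endpoint is the main safeguard. The vascular secondary endpoint of time to resolution (2.2) refers back to the same definition.

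**Working it through.** **1. Can the two classifications disagree?**

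*Neurologic patient:* CRP falls slightly (ESR and SAA too, if all three must improve). Examination, global assessments, MRI and CSF are unchanged.

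| Rule | Element | Met? |
|---|---|---|
| Resolution | Inflammatory item (b in 2.1, D in 5.9.1) | Yes |
| Resolution | No deterioration | Yes, nothing is worse |
| Non-response | No clinical improvement | Yes |
| Non-response | No change on MRI | Yes |
| Non-response | No change in CSF | Yes |

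Inflammatory markers play no part in neurologic non-response, and every element of it is met. The conflict therefore exists whether the list is read as 'and' or 'or', and under either item list.

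*Vascular patient:* both global VAS improve by 15%; CRP and imaging are stable. Item d is met and nothing is worse, so the patient is resolved.
- Under 'or', the VAS gain below 20% alone makes the patient a non-responder, so the classifications conflict.
- Under 'and', non-response also needs aneurysm growth or progression of thrombosis. There is no conflict, but the patient falls in no category, because partial response starts at 20%.

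**2. How easily can noise meet the endpoint?**

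The plan gives no expected rate and no measurement-error data, and section 8.7 gives 10 patients without a calculation. There is no figure to reproduce, and everything below rests on assumptions.

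Assume k = 4 items (as in 2.1) and no true change. Each item improves with probability p, worsens with probability p, and is unchanged with probability u = 1 - 2p. For independent items:
- at least one improves: 1 - (1 - p)^4
- at least one improves and none worsens: (1 - p)^4 - u^4

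| u | p | At least one improves (no bar) | And none worsens (strict bar) |
|---|---|---|---|
| 0 | 0.5 | 1 - 0.0625 = 94% | 0.0625 - 0 = 6% |
| 0.25 | 0.375 | 85% | 15% |
| 0.5 | 0.25 | 68% | 25% |
| 0.75 | 0.125 | 1 - 0.586 = 41% | 0.586 - 0.316 = 27% |

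Correlated items were simulated as 400,000 sets of four equicorrelated normal change scores. A patient qualifies if at least one score improves and none is worse than the bar, in SDs of the change score.

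| Correlation | Any worsening disqualifies | Bar at 1 SD | Bar at 2 SD |
|---|---|---|---|
| 0 | 6% | 49% | 86% |
| 0.3 | 14% | 56% | 82% |
| 0.6 | 23% | 62% | 76% |

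The rates are thus about 6-27% under the strict bar, 49-62% with a 1-SD bar, and up to 94% with no effective bar. With three to five items the full span is about 3% to 97%.

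**3. Would a 20% floor alone cure this?**

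Take within-patient CV c and independent items. The chance that one item improves by 20% or more is p = 1 - Φ(0.20 / (√2 c)). The chance that at least one of four improves that much and none worsens that much is (1 - p)^4 - (1 - 2p)^4.
- c = 10%: p = 0.079, result 22%
- c = 20%: p = 0.240, result 26%
- c = 30%: p = 0.319, result 20%

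A floor on each item still lets about a fifth to a quarter of no-change patients qualify. The any-one-item rule itself has to be tied to the response categories.

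**The case against.** The best defence is that the items are only domains and the response categories are the scored outcome. The categories sit under the same primary-endpoint text, section 3.4 has them determined when the endpoint is assessed, 8.4.1 lists complete responders, and 8.4.2 points to the definitions. Section 8 plans no table of an any-item resolution rate. This narrows the point: a reader might infer that dropped patients will be reported as successes, but no planned analysis says so. It does not remove the conflict, because 2.1 and 5.9.1 still name resolution as the primary endpoint, 8.4.2 words its claim around it, and no section states the link.

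Several stronger readings are tempting and not supported:
- *The endpoint passes or fails almost everyone.* Six separate noisy measures would give 1 - 0.5^6 = 98% and 0.5^6 = 2% for the two extreme readings. Section 2.1, however, groups CRP, ESR and SAA in one item and the two global VAS in another. With four items, ties and intermediate bars, the rates spread across the range shown.
- *Noise would almost certainly produce 5 of 10 successes.* That takes the half-of-patients part of 8.4.2 and drops its 50% response part. It is not a rule in the plan.
- *The vascular conflict is certain.* It depends on reading the list as 'or'.
- *Section 5.9.1 drops global assessment.* It lacks the separate item, but uses VAS and physician global assessment as measurement methods within other items.

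The study is an exploratory pilot that is not powered. That excuses low precision, but not two rules that disagree about one patient.

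**Conclusion.** The concern holds in a limited form. For neurologic patients, the stated rules can class one patient as resolved and as a non-responder to be dropped, on any reading of the non-response list. For vascular patients the conflict arises only under 'or'. This needs no numerical assumption.

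The noise figures (about 6-27%, 49-62%, up to 94%) are illustrations. They assume four items, no true change, and the stated ties, correlations and bars. They show that the undefined deterioration clause largely decides how often a no-change patient qualifies. They do not show that the endpoint is uninformative under every reading, or what the trial's actual rate would be.

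**What to change.** Amend 2.1 and 5.9.1 as follows.
1. State that a patient classed as a non-responder at Day 30 does not meet the primary endpoint, so that resolution means complete or partial response as the plan defines them.
2. Define 'without deterioration': which items it covers and how large a worsening counts.
3. State whether the non-response elements are joined by 'and' or 'or', and how a patient who fits no category is counted. The schedule marks CSF puncture as optional, so say how a neurologic patient without Day 30 CSF is classified.
4. Use one item list in both sections. Align the 50% boundary too: exactly 50% on VAS and CRP counts towards complete response in 2.1 and partial response in 5.9.1.
5. Reconcile the result with 8.4.1-8.4.2, which use complete responders and a 50% rule.

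Any numerical floor for neurologic scales, MRI, ESR or SAA is for the sponsor to set in advance. The 20% figure is a vascular VAS and CRP cut-off, and nothing in the documents extends it to those measures. Inflammatory markers need not be demoted, since the primary objective names inflammatory findings. The dropping rule uses the same categories, so the sponsor must settle their wording with that in view; this review takes no position on it.

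The cost is protocol wording, with no new data collection. The downside is that the reported success percentage may be lower.
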